5.5.1 Non-hematological dose-limiting toxicity

5.5.1.1 Any Grade 3 or greater non-hematological toxicity at least possibly attributable to protocol therapy with the specific exclusion of:

- Alopecia
- Grade 3 fatigue, anorexia, nausea, vomiting, and diarrhea not requiring hospitalization, tube-feeding, or use of TPN.
- Grade 3 liver enzyme elevation, including ALT/AST, occurring after flotetuzumab administration that returns to Grade ≤ 1 or baseline within 7 days from the start of therapy. Note: For the purposes of this study the ULN for ALT is defined as 45 U/L.
- Grade 3 or 4 fever, febrile neutropenia, or infection
- Grade 3 or 4 isolated electrolyte abnormalities that resolve with or without intervention to \leq Grade 2 within 72 hours. Electrolyte supplementation is encouraged.
- Grade 3 or 4 tumor lysis syndrome that resolves within 7 days without end-organ damage.
- Grade 3 rash that resolves (with or without supportive care) to \leq

THIS PROTOCOL IS FOR RESEARCH PURPOSES ONLY, SEE PAGE 1 FOR USAGE POLICY

Grade 2 within 7 days

- Grade 3 mucositis that resolves (with or without supportive care) to \leq Grade 2 within 7 days
- Early intervention with TPN or enteral tube feeding for anorexia, nausea not attributable to protocol therapy, or concern for poor nutritional status clearly and incontrovertibly not attributable to protocol therapy will not be considered a DLT
- Grade 3 or greater pain due to leukemia, mucositis, typhlitis, infection, or obvious injury
- Grade 3 IRR (including CRS) resolving to \leq Grade 2 within 72 hours. CRS will be defined by ASBMT consensus grading³⁶
- Cases of Hy's law ($> 3x$ ULN of ALT/AST along with $> 2x$ ULN in total bilirubin without evidence of cholestasis) will be considered a DLT if no other reason can be found to explain the observed injury (e.g. leukemia, infection, another drug, etc.).

5.5.1.2 Non-hematological toxicity that causes a delay of ≥ 14 days between treatment cycles.

5.5.1.3 Note: Allergic reactions that necessitate discontinuation of study drug will not be considered a dose-limiting toxicity.

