If a patient experiences progressive disease at any time point, they must discontinue protocol therapy. Patients with at least a partial response (PR) following Cycle 2 may continue on subsequent cycles of flotetuzumab for a total of up to 6 cycles. Patients should discontinue protocol therapy if they have not achieved at least a PR following Cycle 2. No planned step-up dosing will occur during subsequent cycles unless there is an infusion interruption of > 3 days between cycles of flotetuzumab. For patients with no evidence of disease after Cycle 1, subsequent cycles should be interrupted until ANC $\geq 500 \mu\text{L}$ and platelets $\geq 20,000/\text{mm}^3$. Patients with persistent disease are permitted to continue flotetuzumab regardless of ANC and platelet counts.

Pharmacokinetic sampling and monitoring for ADAs will be performed in all patients (see [Appendix VI-A](#), [Appendix VI-B](#), [Appendix VI-C](#), and [Appendix VII](#)). In consenting patients, correlative studies to characterize the tumor microenvironment will be obtained, which will include peripheral blood studies and bone marrow (see [Appendix X](#) and [Appendix XII](#)). Correlative plasma studies as a measurement of CRS and biomarkers of response will also be obtained in consenting patients (see [Appendix XI](#)).

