5.3.2 Intra-Patient Escalation

Intra-patient dose escalation will occur during the first 7 days of Cycle 1 on Dose Level 1 and the first 8 days of Cycle 1 on Dose Levels -1 and 2 as described in [Section 5.1](#). Intra-patient dose escalation occurring outside of this time period is not allowed.

5.4 **Grading of Adverse Events**

Adverse events (toxicities) will be graded according to the NCI Common Terminology Criteria for Adverse Events (CTCAE) version 5.0. All appropriate treatment areas should have access to a copy of the CTCAE version 5.0. A copy of the CTCAE version 5.0 can be downloaded from the CTEP website (http://ctep.cancer.gov/protocolDevelopment/electronic_applications/ctc.htm). Any suspected or confirmed dose-limiting toxicity should be reported immediately (within 24 hours) to the Study Chair.

5.5 **Definition of Dose-Limiting Toxicity (DLT)**

DLT will be defined as any of the following events that are possibly, probably or definitely attributable to protocol therapy. The DLT observation period for the purposes of dose-escalation will be the first cycle of therapy.

Dose limiting hematological and non-hematological toxicities are defined differently.

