5.5.2 Hematological dose limiting toxicity

Hematological dose limiting toxicity will be defined as failure to recover a peripheral ANC $> 500/\text{mm}^3$ and platelets $> 20,000/\text{mm}^3$ by 42 days after the first treatment day. Patients with detectable leukemia (inclusive of MRD) will be unevaluable for a hematologic DLT.

5.5.2.1 Note: Grade 3 or 4 febrile neutropenia will not be considered a dose-limiting toxicity.

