11.2 Definitions

11.2.1 Evaluable For Adverse Events

Any patient who receives at least one dose of the study drug(s) or who experiences a dose-limiting toxicity is considered evaluable for Adverse Events. In addition, for the dose-escalation portion during Cycle 1, patients must receive at least 80% of the prescribed dose per protocol guidelines and must have the appropriate toxicity monitoring studies performed to be considered evaluable for dose limiting toxicity. Patients who do not have DLT and are not considered evaluable for toxicity will be replaced.

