12.2 Response Criteria for Patients with Leukemia

Patients must have received ≥ 1 cycle of flotetuzumab, be evaluable for DLT, and have had ≥ 1 bone marrow evaluation(s) following treatment. Response will be defined as best response after up to 4 cycles. The AML response criteria are derived from the revised AML International Working Group (IWG) Criteria.³⁸ It is anticipated that patients who achieve morphologic remission with study treatment may proceed to subsequent allogeneic HSCT at the treating physician's discretion.

THIS PROTOCOL IS FOR RESEARCH PURPOSES ONLY, SEE PAGE 1 FOR USAGE POLICY

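### The 14-day-delay DLT cannot be met by a child who has no second cycle due, yet that child still counts as DLT-free; the gap is narrow and its size unknown, but the scoring should not depend on response

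*Combined protocol and SAP*

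**What the plan says.** Section 5.5.1 gives two routes to a non-hematological DLT. Section 5.5.1.1 covers "Any Grade 3 or greater non-hematological toxicity at least possibly attributable to protocol therapy with the specific exclusion of" a list of exceptions. Section 5.5.1.2 adds "Non-hematological toxicity that causes a delay of ≥ 14 days between treatment cycles". Section 5.5 fixes the window: "The DLT observation period for the purposes of dose-escalation will be the first cycle of therapy".

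A child may complete Cycle 1 and have no Cycle 2. Section 2.5 says: "If a patient experiences progressive disease at any time point, they must discontinue protocol therapy". Section 12.2 anticipates that "patients who achieve morphologic remission with study treatment may proceed to subsequent allogeneic HSCT at the treating physician's discretion". Section 10.1 also allows removal by family refusal or physician decision.

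Evaluability for DLT under 11.2.1 looks only at Cycle 1: "patients must receive at least 80% of the prescribed dose per protocol guidelines and must have the appropriate toxicity monitoring studies performed". On replacement it says: "Patients who do not have DLT and are not considered evaluable for toxicity will be replaced". Being due a second cycle is not a condition.

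The hematological DLT in 5.5.2 is written differently. It is tied to a fixed day, 42 days after the first treatment day, and it says who cannot be scored: "Patients with detectable leukemia (inclusive of MRD) will be unevaluable for a hematologic DLT". Section 5.5.1.2 has neither feature, and no other section says how to score it when no Cycle 2 is due.

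**The concern.** Section 5.5.1.2 detects persistent toxicity through its effect on the start of the next cycle. Take two children with the same attributable toxicity, neither having a DLT under 5.5.1.1, and both still above the restart limits 14 days after the planned start of Cycle 2. The one due Cycle 2 has a DLT. The one whose Day 29 marrow showed progression has none, and enters the column of patients without DLT in the 11.3 table and the one-third test in 11.2.2.

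The scored DLT rate then depends partly on how the leukemia responded. Removing one route to a DLT for some evaluable children can only lower that rate. Decisions turn on one or two events in up to six children, so one child scored differently can change a dose decision.

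**Working it through.** **Plan's own sizes.** Three levels of 6 plus 6 PK patients is 24, and 24/0.9 = 26.7, giving 27. Three levels of 12 plus 6 is 42, and 42/0.9 = 46.7, giving 47. Both stated maxima reproduce.

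**What falls outside 5.5.1.1 but can block Cycle 2.** Section 5.2 requires the eligibility laboratory parameters to be met before a subsequent cycle. Section 4.1.8.3 and Appendix III give:

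| Test | Limit to restart | Grade 2 range |
|---|---|---|
| ALT | 3 × 45 = 135 U/L | 136–225 U/L |
| Bilirubin | 1.5 × ULN | above 1.5 to 3.0 × ULN |

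- Isolated Grade 2 ALT or bilirubin is below Grade 3, so it is not a DLT under 5.5.1.1, but it blocks Cycle 2. If it lasts 14 days, 5.5.1.2 is the only route by which it counts. ALT or AST above 3 × ULN together with bilirubin above 2 × ULN, without cholestasis or another explanation, is already a DLT under the Hy's law item.
- Grade 3 or 4 infection is excluded from 5.5.1.1 with no time limit. If attributable and prolonged, 5.5.1.2 is its only non-hematological route.
- Excluded electrolyte changes and IRR/CRS must settle within 72 hours, and excluded liver enzymes, tumor lysis, rash and mucositis within 7 days. When they do not, they are DLTs without any second cycle.

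**Timing.** Day 29 + 14 = Day 43, or 29 + 3 + 14 = Day 46 if the delay is counted after the optional respite. Both lie beyond the 29-day cycle named as the DLT window. Both fall before off-study at about 29 + 30 = Day 59 for an infusion that ends on Day 29.

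**Illustration of size.** All rates here are assumptions:
- other DLTs, b = 20%;
- q = rate of the toxicity that only 5.5.1.2 would catch;
- f = share of children with no Cycle 2, taken as 1/3.

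With independent events the scored rate is p = 1 − (1 − b)(1 − q(1 − f)). The chance that six children show at most 1 DLT is (1 − p)^6 + 6p(1 − p)^5.

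| q | p, all scorable | P(≤1 of 6) | p, f = 1/3 | P(≤1 of 6) | Rise (points) |
|---|---|---|---|---|---|
| 1% | 20.8% | 0.636 | 20.5% | 0.642 | 0.7 |
| 2% | 21.6% | 0.616 | 21.1% | 0.629 | 1.3 |
| 3% | 22.4% | 0.597 | 21.6% | 0.616 | 2.0 |
| 5% | 24.0% | 0.558 | 22.7% | 0.590 | 3.2 |
| 10% | 28.0% | 0.464 | 25.3% | 0.526 | 6.2 |
| 15% | 32.0% | 0.378 | 28.0% | 0.464 | 8.6 |

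If the two kinds of DLT never overlap, p = b + q(1 − f). For q = 5%, 10% and 15% the chance then goes from 0.534 to 0.574, 0.420 to 0.495 and 0.319 to 0.420, a rise of 4.0, 7.5 and 10.1 points.

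**The case against.** The strongest reply is that very little is lost. Most serious toxicity is a DLT under 5.5.1.1 whether or not a second cycle follows, so a reader who infers that all unresolved toxicity goes unscored in children who stop is reading too much into the text. That stands, and it confines the point to the narrow group above. For so narrow a group, rates of 1% to 3% are as plausible as 5% to 15%, and the documents support neither.

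A reader might also take the share without Cycle 2 from the adult data in Section 2.3.1: 9 of 27 (33%) without anti-leukemic activity, or 14 of 27 (52%) after adding the 5 with CR/CRi. The documents do not support this. Lack of activity is not progression, children with stable disease may continue to Cycle 2 (Section 11.1), and failure to reach PR ends therapy only after Cycle 2. The CR/CRi count is not a Cycle 1 result, and Section 12.2 does not say that transplant follows Cycle 1. The one third used above is therefore only an assumption. Children who receive less than 80% of Cycle 1 without a DLT are replaced, so they are not part of the problem.

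Nor can one say that the bias is larger at doses where more children progress. A dose with more remissions could send more children to transplant, so the net direction across doses is unknown.

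One further reply is that Section 5.2 lets children start Cycle 2 while the marrow result is pending, so they meet the delay test before progression is known. This helps little: children able to start at once do not have the blocking toxicity, and those who have it are the ones still waiting when the result arrives.

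Finally, adverse events within 30 days of the last dose are already followed and reported (Section 10.1), and DLT evaluations are reviewed weekly (Section 14.3.2). So the data largely exist, and what is missing is the scoring rule.

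**Conclusion.** The point holds in limited form. Section 5.5.1.2 cannot be met by a child who completes enough of Cycle 1 to be evaluable and then has no Cycle 2, and the plan counts that child as DLT-free. This follows from the text and needs no assumed rate. It affects only toxicity outside 5.5.1.1.

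The scored DLT rate is biased downward by an unknown amount. With other DLTs at 20% and one third of children unscorable, the chance that a cohort of six passes rises by about 1 to 2 points if such toxicity occurs in 1% to 3% of children. At 5% to 15% the rise is about 3 to 9 points (independent events) or 4 to 10 (non-overlapping events). No gradient across dose levels can be claimed. The change is worth making because it is cheap and removes a dependence of DLT scoring on disease response.

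**What to change.** - Keep the 14-day threshold and the plan's own restart requirements. Reword 5.5.1.2 to score attributable non-hematological toxicity that prevented, or would have prevented, the start of Cycle 2 for 14 days or more after its planned start, whether or not Cycle 2 is given. Section 6.2.3 already counts from the planned start of the next cycle.
- State that a child who starts new anti-leukemia therapy, or goes off study, before that day with the toxicity unresolved is not evaluable for this criterion, as 5.5.2 does for the hematological DLT. Report the number of such children at each dose level. Without this, they would still be counted silently as free of this DLT. Enrollment on another COG therapeutic study (Section 10.2) is one way it can happen.
- Reconcile the criterion with the first-cycle DLT window in Section 5.5, and say whether the planned start is Day 29 or follows the optional respite of up to 3 days in Section 5.2.

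The cost is one reworded criterion, one adverse-event status check inside the existing 30-day follow-up, and a slightly higher observed DLT rate. The planned maxima of 27 and 47 do not change, provided these children are reported and not replaced.

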5.5.2 Hematological dose limiting toxicity

Hematological dose limiting toxicity will be defined as failure to recover a peripheral ANC $> 500/\text{mm}^3$ and platelets $> 20,000/\text{mm}^3$ by 42 days after the first treatment day. Patients with detectable leukemia (inclusive of MRD) will be unevaluable for a hematologic DLT.

5.5.2.1 Note: Grade 3 or 4 febrile neutropenia will not be considered a dose-limiting toxicity.

6.0 DOSE MODIFICATIONS FOR ADVERSE EVENTS

The Study Chair must be notified of any dosage modification or use of myeloid growth factor.

6.1 Dose Modifications for Hematological Toxicity

- 6.1.1 Patients who have dose-limiting thrombocytopenia or neutropenia should receive subsequent cycles at the next lower dose level.
- 6.1.2 Patients who experience dose-limiting thrombocytopenia or neutropenia after one dose reduction must be removed from protocol therapy. The use of hematopoietic growth factors is discouraged. However, granulocyte colony stimulating factor may be used outside of Cycle 1 for culture proven bacteremia or invasive fungal infection. The Study Chair should be notified before growth factors are initiated.
- 6.1.3 Patients who have a dose-limiting hematological toxicity that does not resolve to eligibility parameters within 56 days of any cycle in the absence of

THIS PROTOCOL IS FOR RESEARCH PURPOSES ONLY, SEE PAGE 1 FOR USAGE POLICY
detectable leukemia must be removed from protocol therapy.

6.2 Dose Modifications for Non-Hematological Toxicity

- 6.2.1 Patients who have any dose-limiting non-hematological toxicity (as defined in [Section 5.5.1](#)) may continue on protocol therapy upon meeting eligibility lab requirements or baseline but should receive subsequent doses at the next lower dose level.
- 6.2.2 If a non-hematological dose-limiting toxicity recurs after one dose reduction, the patient must be removed from protocol therapy.
- 6.2.3 Patients who have a dose-limiting non-hematological toxicity that does not resolve to baseline or eligibility within 21 days after the planned start of the next treatment cycle must be removed from protocol therapy.

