5.3 Dose Escalation Schema

5.3.1 Inter-Patient Escalation

The starting dose will be 500 nanograms/kg/day (DL1) with dose levels for subsequent groups of patients as follows:

Dose Level	Dose (nanograms/kg/day)
-1	300
1*	500
2	700

* Starting Dose Level

THIS PROTOCOL IS FOR RESEARCH PURPOSES ONLY, SEE PAGE 1 FOR USAGE POLICY

There will be no planned escalations beyond Dose Level 2 (700 nanograms/kg/day), as previous pediatric Phase 1 studies have rarely defined a MTD greater than 160% of the adult MTD. If estimated clearance is high in this pediatric study population, we will consider amending the protocol to allow further dose escalation to 900 nanograms/kg/day.

If the MTD has been exceeded at the first dose level, then the subsequent cohort of patients will be treated at a dose of 300 nanograms/kg/day (Dose Level -1). If Dose Level -1 is not well tolerated, further de-escalation will not occur. The study will be closed to accrual.

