6.3.1 CRS Management

The following are treatment guidelines (which may be modified as needed by the responsible investigator according to the best practices of medicine) for CRS related to flotetuzumab. Early intervention at the first signs of CRS, including pyrexia, tachycardia, tachypnea and/or hypotension in the absence of alternative etiologies and in consistent temporal relationship to administration of flotetuzumab, should be undertaken.

CRS is a commonly observed event during treatment with flotetuzumab based on experience in the adult population, with the majority of patients experiencing at least 1 event of Grade 1 or 2. Based on current understanding gained from patients treated with blinatumomab and CAR T cells, CRS is likely to be a common toxicity that can be managed through supportive care and anti-cytokine interventions to allow for full activity of T cells during therapy. A consensus grading system for CRS has been proposed by the American Society for Blood and Marrow Transplantation which will be utilized for this study ([Table 1](#)).

Table 1: ASBMT CRS Consensus Grading

CRS Parameter	Grade 1	Grade 2	Grade 3	Grade 4
Fever*	Temperature \geq 38°C	Temperature \geq 38°C	Temperature \geq 38°C	Temperature \geq 38°C
		With		
Hypotension	None	Not requiring vasopressors	Requiring a vasopressor with or without vasopressin	Requiring multiple vasopressors (excluding vasopressin)
		And/or [#]		
Hypoxia	None	Requiring low-flow nasal cannula ^{#@} or blow-by supplemental oxygen	Requiring high-flow nasal cannula ^{#@} , facemask, non-rebreather mask, or Venturi mask supplemental oxygen	Requiring positive pressure (e.g., CPAP, BiPAP, intubation and mechanical ventilation)

Organ toxicities associated with CRS may be graded according to CTCAE v5.0 but they do not influence CRS grading.

*Fever is defined as temperature \geq 38°C not attributable to any other cause. In patients who have CRS then receive antipyretic or anticytokine therapy such as tocilizumab or steroids, fever is no longer required to grade subsequent CRS severity. In this case, CRS grading is driven by hypotension and/or hypoxia.

[#]CRS grade is determined by the more severe event: hypotension or hypoxia not attributable to any other cause. For example, a patient with temperature of 39.5°C, hypotension requiring 1 vasopressor, and hypoxia requiring low-flow nasal cannula is classified as grade 3 CRS.

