- Grade 3 CRS that is refractory to tocilizumab should be treated with corticosteroids. Dexamethasone is the corticosteroid of choice administered at a total daily dose of at least 0.2 – 0.4 mg/kg/day (maximum 24 mg per day) administered preferably intravenously divided 3 – 4 times daily for at least 1 day but no more than 4 days. The dose should be stopped or tapered as clinically indicated.
- If infusion reaction improves to \leq grade 2 within 72 hours, infusion may be resumed at no greater than 50% of the original rate once symptoms decrease to Grade 1. The rate may then be escalated to the original rate after 30 minutes, as tolerated. A more gradual increase in the rate of infusion may be undertaken after consultation with the study chair;
- If infusion reaction DOES NOT improve to \leq grade 2 within 72 hours or if there are multiple grade 3 infusion reactions, flotetuzumab treatment must be permanently discontinued:
 - Report as an immediately reportable event (IRE) immediately;
 - Report the event as a serious adverse event (SAE) if appropriate.

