6.3.1.4 Grade 4 Infusion Reactions and Infusion-Related Events

- Stop the infusion and disconnect the infusion tubing from the patient;
- TO AVOID EXACERBATION OF INFUSION REACTION OR CRS: DO NOT FLUSH THE TUBING – ASPIRATE RESIDUAL DRUG FROM THE PORT LUMEN;
- Administer IV fluids, diphenhydramine IV, acetaminophen PO/IV for fever, and oxygen and bronchodilators for mild bronchospasm, as appropriate.
- Provide appropriate ventilator and circulatory support as medically indicated;
- Agents including those listed below have been described in the management of patients with severe complications of cytokine storm and/or severe immune-related adverse events, and may be required:
 - Higher doses of corticosteroids and/or
 - Tocilizumab (anti-IL-6 receptor):
 - <30 kg: 12 mg/kg IV
 - ≥ 30 kg: 8 mg/kg [max 800 mg] IV, and/or
 - Etanercept (anti-TNF α) 0.8 mg/kg (max: 50 mg/dose) subQ
- Notify the Sponsor's Medical Monitor immediately;
- Report the event as an SAE. Patients who have a Grade 4 CRS should not receive further flotetuzumab.

THIS PROTOCOL IS FOR RESEARCH PURPOSES ONLY, SEE PAGE 1 FOR USAGE POLICY

6.3.1.5 Grade 5 Infusion Reactions and Infusion-Related Events:

- Notify the Sponsor's Medical Monitor or designee immediately;
- Report the event as an SAE.

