9.3 Useful Links and Contacts

- CTEP Forms, Templates, Documents:
<http://ctep.cancer.gov/forms/>
- NCI CTEP Investigator Registration:
[contact]
- CTEP Identity and Access Management (IAM) account:
<https://ctepcore.nci.nih.gov/iam/>
- CTEP Associate Registration and IAM account help:
[contact]
- IB Coordinator:
[contact]

10.0 CRITERIA FOR REMOVAL FROM PROTOCOL THERAPY AND OFF STUDY CRITERIA**10.1 Criteria for Removal from Protocol Therapy**

- a) Clinical (including physical examination or serum tumor markers) or radiographic

THIS PROTOCOL IS FOR RESEARCH PURPOSES ONLY, SEE PAGE 1 FOR USAGE POLICY

evidence of progressive disease (See [Section 12](#)).

- b) Have not achieved at least a PR following 2 successive treatment cycles.
- c) Adverse Events requiring removal from protocol therapy (See [Section 13](#)).
- d) Development of a DLT following 1 dose reduction.
- e) An infusion stop or delay of more than 2 weeks due to AE or more than 2 discontinuations per cycle due to AE (does not apply for prolongation of the scheduled treatment free period of a cycle).
- f) Refusal of protocol therapy by patient/parent/guardian
- g) Non-compliance that in the opinion of the investigator does not allow for ongoing participation.
- h) Completion of 6 cycles of therapy.
- i) Physician determines it is not in the patient's best interest.
- j) Repeated eligibility laboratory studies (CBC with differential, bilirubin, ALT (SGPT) or serum creatinine) are outside the parameters required for eligibility prior to the start of flotetuzumab (See [Section 8.1](#)).
- k) Study is terminated by Sponsor.
- l) Pregnancy

Patients who are removed from protocol therapy during Cycle 1 should continue to have the required observations in [Section 8.1](#) until the originally planned end of the cycle or until all adverse events have resolved per [Section 13.4.4](#), whichever happens LATER. The only exception is with documentation of the patient's withdrawal of consent. Patients who are removed from protocol therapy in subsequent cycles should have the necessary observations to ensure adequate clinical care.

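### Section 6.2.1 lets patients continue after cytokine release DLTs for which Sections 6.3.1.3 and 6.3.1.4 end flotetuzumab, and the protocol does not say which rule governs

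*Combined protocol and SAP*

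**What the plan says.** **DLT definition (5.5.1.1).** Attributable non-hematological toxicity of Grade 3 or higher is a DLT. The only IRR/CRS exclusion is a Grade 3 event that comes down to Grade 2 or lower within 72 hours.

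**General rule (6.2.1).** It opens "Patients who have any dose-limiting non-hematological toxicity (as defined in" Section 5.5.1, and says that these patients "may continue on protocol therapy upon meeting eligibility lab requirements or baseline but should receive subsequent doses at the next lower dose level". Removal follows if a DLT recurs after one reduction (6.2.2), or if it is unresolved 21 days after the next cycle was due (6.2.3).

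**IRR/CRS rules (6.3.1).** The section introduces its content as "treatment guidelines (which may be modified as needed by the responsible investigator according to the best practices of medicine". For a Grade 3 reaction not down to Grade 2 within 72 hours, "or if there are multiple grade 3 infusion reactions, flotetuzumab treatment must be permanently discontinued" (6.3.1.3). For Grade 4: "Patients who have a Grade 4 CRS should not receive further flotetuzumab" (6.3.1.4).

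**Starting a further cycle (5.2).** The patient must qualify to continue under Section 6.0.

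**Removal list (10.1).** Item (c) is "Adverse Events requiring removal from protocol therapy", with a reference to Section 13. Item (d) is a DLT after one dose reduction. Item (e) includes "more than 2 discontinuations per cycle due to AE".

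**Lowest level (5.3.1).** "If Dose Level -1 is not well tolerated, further de-escalation will not occur".

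**The concern.** Two parts of Section 6 give opposite answers for the same event. A child with Grade 4 CRS, or with Grade 3 CRS that outlasts 72 hours, may go on at a lower dose under 6.2.1 and receives no more drug under 6.3.1. The permission stands in unqualified text, while the stops stand in text that the investigator may modify.

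CRS was the most common treatment-related event in the adult trial (2.3.1), and safety is primary aim 1.1.1. Two sites could each point to a section that supports them, yet one re-exposes a child after a severe reaction and the other does not. Safety and response data from later treatment would then depend partly on which section a site had read.

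**Working it through.** No design calculation underlies this point, so the check is to run the same patient through each section.

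**Step 1: do the rules cover the same events?** Section 5.5.1.1 exempts Grade 3 IRR/CRS only if it reaches Grade 2 or lower within 72 hours. Section 6.3.1.3 stops treatment when that same threshold is missed. Every attributable prolonged Grade 3 CRS is therefore both a DLT (6.2.1 applies) and a stop (6.3.1.3 applies). Grade 4 CRS is a DLT with no exemption, and 6.3.1.4 applies to it.

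**Step 2: scenarios** (no earlier dose reduction).

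| Event | DLT? | 6.2.1 | 6.3.1 | 10.1(d), (e) |
|---|---|---|---|---|
| Grade 4 CRS, infusion stopped 5 days | Yes | May continue, one level down | No further drug | Not triggered |
| Grade 3 CRS lasting 96 h, stopped 5 days | Yes | May continue, one level down | Permanent stop | Not triggered |
| Two Grade 3 CRS in one cycle, 48 h each | No | Does not apply | Permanent stop, if two counts as multiple | Not triggered (needs more than 2) |
| One Grade 3 CRS, 48 h | No | Does not apply | May resume | Not triggered |

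The first two rows are the direct conflict. The third is a question of definition: 6.3.1.3 does not say how many reactions are multiple. The fourth shows no conflict.

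**Step 3: does another section settle it?** Section 5.2 sends the reader to Section 6.0 as a whole, which contains both rules, and it applies only at the start of a cycle. Section 6.2.1 speaks of later doses, where 6.1.1 speaks of later cycles, so 6.2.1 can be read as reaching resumption within a cycle. Section 10.1(c) points to Section 13, which holds reporting rules and no removal criteria.

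**Step 4: DL-1.** The levels are 300, 500 and 700 ng/kg/day. A child assigned to 300 who has a first DLT is directed by 6.1.1 or 6.2.1 to a lower level that does not exist. Section 10.1(d) does not apply, because no reduction has occurred.

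**Step 5: how many children?**
- Adult Grade 3 or higher IRR/CRS at 500 ng/kg/day (2.3.1): 4/31 = 12.9%.
- Maximum anticipated enrollment (11.1): 27.
- 27 × 4/31 = 3.5 children with a Grade 3 or higher event.
- Median duration of those adult events: 2.5 days × 24 = 60 hours, against the 72-hour limit.

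The 3.5 counts all Grade 3 or higher events. The documents do not separate Grade 4 from Grade 3, or say how many events outlasted 72 hours or recurred. They also do not say whether the 2.5 days is time at Grade 3 or higher or time to full resolution. The share that meets the conflict cannot be calculated.

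**The case against.** The best reply is that 6.3 is the section specific to IRR/CRS and a specific rule normally overrides a general one. Section 6.2.1 only permits continuation, so a site that stops treatment breaks neither rule. Section 5.2 adds that a child barred by any part of Section 6 cannot start a new cycle. There is also central control: DLTs go to the study chair within 24 hours (5.4), dosage changes must be notified (6.0), Grade 4 reactions go to the medical monitor at once (6.3.1.4), and evaluations are reviewed weekly (14.3.2).

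Much of this stands. It makes divergence between sites less likely and gives a sensible way to read the text. It does not remove the conflict, because the protocol never states that precedence, and the section that would prevail describes itself as modifiable. Oversight can catch a difference, but those exercising it work from the same text.

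Four stronger readings are tempting and not supported:

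- **That 10.1 is a third, competing rule set.** It is a list in which any one item is enough for removal. It is silent on the CRS stops and nowhere permits continuation against them. Its weaknesses are the reference in (c) and the unexplained difference between multiple reactions in 6.3.1.3 and more than two discontinuations in (e), which also counts stops for any adverse event.
- **That up to 9 children are affected (27 × 3/9).** This applies the rate at 700 ng/kg/day to everyone, although accrual starts at 500 and the 27 covers three levels, PK expansion and attrition. Of the three adults, only one is listed as CRS; the others had syncope and arthralgia/myalgia.
- **That every DLT at 300 ng/kg/day lacks a rule.** A child reduced to that level whose DLT recurs is removed under 6.2.2 and 10.1(d). The gap concerns a first DLT in a child assigned there, and that cohort opens only if 500 is not tolerated.
- **That the MTD is compromised.** DLTs for escalation are counted in Cycle 1 under 5.5, whichever continuation rule is followed.

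**Conclusion.** The conflict between 6.2.1 and Sections 6.3.1.3 and 6.3.1.4 is literal and covers all Grade 4 CRS and all Grade 3 IRR/CRS not down to Grade 2 within 72 hours, when attributed to protocol therapy. It does not extend to other non-hematological DLTs, or to a single Grade 3 reaction that settles within 72 hours.

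Its size in patients is unknown. If children have the adult rate at 500 ng/kg/day, about 3.5 of 27 would have a Grade 3 or higher event, and those in conflict are some part of that. The rate at 700 could differ, and the documents give no usable figure for it.

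The effect is on patient safety and on whether continued exposure is handled alike across sites. Dose-escalation decisions do not depend on it. Any effect on later PK is small, since sampling is in Cycle 1 and at the end of therapy (8.2.2), and response is reported only descriptively (11.5). The reference in 10.1(c), the undefined count in 6.3.1.3 and the DL-1 gap are secondary. A safety stopping rule should still not depend on an unstated order of precedence.

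**What to change.** Reconcile the passages, with the sponsor deciding the clinical content:

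1. In 6.2.1, state whether it applies to IRR/CRS DLTs covered by 6.3.1.3 and 6.3.1.4, and which section governs them, including resumption within a cycle.
2. In 6.3.1, state whether the stops for Grade 3 and Grade 4 reactions are mandatory or fall under the modifiable guidance.
3. Point 10.1(c) to the removal rules in Section 6.
4. Define the count meant by multiple Grade 3 reactions in 6.3.1.3, and state how it relates to 10.1(e).
5. In 6.1.1 and 6.2.1, state what applies to a first DLT in a patient assigned to DL-1.

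The cost is an amendment of wording. It needs no added patients, visits or data, and no change to the escalation design.
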